All primary analyses will follow an intent-to-treat approach, including all individuals assigned to an intervention arm regardless of the amount of intervention received. Non-inferiority evaluations will also be evaluated in a supplementary “as treated” analysis, comparing outcomes according to treatments actually received by patients during their observed period of follow-up. This supplemental comparison is useful in a non-inferiority assessment due to the fact that the alternative hypothesis of “no effect” is more likely in the presence of protocol violations and therefore the intent to treat approach will be anti-

conservative if many patients in the intervention arm, for example, revert to control. Also, non-inferiority of Emergency Department visit rate in the intervention arm compared to usual care control will only be assessed on final analysis if superiority is shown for the primary endpoint of no antipsychotic use at 6 months.

We will use Poisson regression to estimate (1) the percent of individuals using antipsychotics at 6 months post enrollment and (2) the total number of person-months of antipsychotic use by youth in the six month follow-up period, per provider medication orders, in each of the study arms. We will use generalized estimating equations(43) to estimate the parameters in the Poisson regression model. We will use the robust sandwich estimator to ensure correct standard errors for the intervention effect due to possible violation of the Poisson variance assumption(44); additionally, this will allow us to account for any clustering within clinics(43) and providers. Poisson regression allows comparison of relative incident rates among the intervention arms when outcomes are not rare(45). Additionally, Poisson regression will allow us to control for pre-specified baseline covariates (age, gender, and race) as well as site differences in any antipsychotic use and allow for straightforward estimation of site-specific intervention effects in sensitivity analyses. For a secondary analysis, we will repeat this approach defining antipsychotic use with prescription fill data rather than orders.

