Data for our primary outcome of interest, any antipsychotic use, will be collected from electronic health records on provider orders. Electronic health record data on prescription fills will be used to assess the secondary outcome (antipsychotic medication fills). This means that traditional study drop-out due to premature participant withdrawal from the study will not lead to missing data in primary analyses. However, there will be the potential for differential follow-up rates among individuals due to youth disenrolling from their or their parent/guardian's health plan. Death is also a possibility, but unlikely. We will compare those youth for whom we are only able to collect outcome information for a portion of the 6 month follow-up period to those participants for whom we have complete 6 month follow-up information on their demographics, treatment group, and other salient baseline variables. We will account for differential follow-up times due to disenrollment in the Poisson regression model using an offset(46). Because our power calculations are based on excluding all individuals lost-to-follow-up due to disenrollment, these estimates are conservative.

The secondary outcome of emergency department visits will be estimated by Poisson regression in each of the arms, again using generalized estimating equations for the reasons listed above for the primary outcome. The intervention will be compared for non-inferiority to control using a margin of $M=1.5$. This margin of 1.5 for the rate ratio represents a threshold for the relative increase of 50%, beyond which we would consider unacceptable. Sikirica (2014) observed an annual rate of 0.39 per year among adolescents with attention deficit/hyperactivity disorder who were taking antipsychotics(47). Using an estimated rate of emergency department visits of 0.0325 per month on control(47), the non-inferiority margin of 1.5 for the incidence rate ratio would represent a corresponding maximum acceptable rate of 0.0488 per month in the intervention arm. If the rate of emergency department use is greater than expected, say 0.05, then the non-inferiority margin of 1.5 would correspond to a maximum rate of 0.075 in the intervention arm. The estimated treatment effect (emergency department rate on algorithm

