As these power calculations are based on the assumed percent of participants on any antipsychotic in the control arm and assumed pattern of intervention effects, we provide examples of detectable intervention effects corresponding to alternative scenarios in the table that follows, including varying rates of subgroup prevalence to evaluate power regarding intervention effectiveness in less prevalent minority groups. In summary, at a range of percentages of participants with any antipsychotic use in the control arm, we will have excellent power to detect a variety of clinically meaningful intervention effects within the expected range.

Using an estimated rate of emergency department visits of 0.0325 per month on control(47) and with a one-sided 0.025 alpha level with equal allocation between groups, we estimate 71% power(48) with 400 patients per arm and 67% power with 360 patients per arm (allowing for loss to follow-up) respectively, to detect equality of emergency department visit rates (i.e., a true rate ratio of 1) in a non-inferiority evaluation with a margin of 1.5. With a greater monthly emergency department rate of 0.05, we would have 88% and 84% power with 400 and 360 patients per arm respectively under otherwise equivalent conditions.

Power under varying percentages of participants in each arm taking antipsychotic medication at 6 months (based on medication orders) and under various subgroup prevalence assumptions.

Subgroup prevalence	n per arm*	Intervention	Control	Power
100%	360	89%	95%	80%
100%	360	85%	95%	>99%
100%	360	80%	90%	97%
100%	360	75%	85%	92%
25%	90	82%	95%	80%
18%	65	78%	95%	80%
10%	36	75%	95%	67%
5%	18	65%	95%	62%

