We will compare the outcomes of patients initially prescribed an antipsychotic medication from intervention providers versus control providers. We plan to conduct an intent-to-treat analysis i.e. if a patient is enrolled when an intervention provider issues a qualifying prescription, the patient is enrolled in the intervention arm and, even if the patient sees a control provider at some point, the patient will remain in the intervention arm. Intervention arm is a binary treatment assignment that should be indicated for all enrolled patients in the analytic dataset.

Baseline Covariates

Baseline covariates for this study include: age, gender, race, ethnicity, site, type of insurance (Medicaid/Commercial/Other i.e. self-paid), any inpatient hospitalization in the prior year, provider type and new health plan enrollee (defined as person who does not have 2 or more encounters at least 60 days apart in the year prior to their prescription order date). This definition of new health plan enrollee will be compared to an alternate definition in the three sites with health plan enrollment data: < 105 days enrolled in the health care plan before randomization date). Note that gaps in enrollment less than 45 days count towards the total of 105. Gaps in enrollment ≥ 45 days do not count towards the total of 105, nor does any enrollment prior to the gap ≥ 45 days. Any inpatient hospitalization in the prior year (-1 to -365 days from randomization date) will be adjusted for in primary analyses as it is prognostic of the outcome and will increase precision.

Health plan enrollment and follow-up time

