Inferential analysis: For these analyses, we have data that shows the frequency of emergency visits and frequency of urgent care separately, the outcomes. The main predictor is the treatment arm (intervention or control). We will have one record per patient, which shows the total number of ED or UC visits throughout the study (maximum of 6 months). We will perform Poisson regression analyses, where the outcome is the frequency of ED or UC visits for each enrolled patient and the offset is the number of days follow-up. The treatment arm and inpatient hospitalization in the prior year will be the only covariates included in the regression model, and the estimated coefficient for treatment arm is interpreted as the log-RR of visiting ED or UC more/less frequently, for an intervention patient vs. a control patient. Patient will be the unit of

Analysis plan for Safety Use of Antipsychotics in Youth (SUAY)

analysis for this regression model, and the regression model will be fit using generalized estimating equations (GEE) to account for correlation within provider. We will estimate standard errors using a robust (sandwich) covariance estimation and construct a 95% confidence interval (CI) around the estimated RR. The estimated RR and two-sided confidence interval will be compared to the non-inferiority margin, $M=1.5$, and non-inferiority of the intervention will be concluded if the entire coverage of the 95% CI is less than 1.5.

Variables	Definition	Present/Absent
ed_uc	This is the number of days with emergency department and/or urgent care visits that occurred during the study, from the enrollment date to 6 months post-enrollment	absent
group	Randomization Group – use for restricted descriptive stats (Intervention/Control)	present
group_cat	Randomization Group – use in models (Control (0)/Intervention (1))	present
e_offset	Number of days of follow-up for ED/UC analysis	absent
prior_hosp	Prior Hospitalization (No (0)/Yes(1))	present

Secondary analysis II

Percentage of youth with baseline and follow-up safety assessments (i.e., BMI measurement and laboratory measure/orders)

For these analyses, we will measure safety assessments of BMI and laboratory (Lipids, cholesterol, Hb1ac, prolactin, and any labs (at least 1)) measure/orders:

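### The ED/urgent-care non-inferiority model omits the patient's own prior-year ED/urgent-care use, and the protocol's power for that test is an upper limit at the rates it assumes

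*SAP*

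**What the plan says.** SAP, Secondary analysis I, fits a Poisson regression by GEE to each patient's ED/urgent-care count over up to 6 months, with a follow-up offset and robust standard errors. Non-inferiority is concluded if the whole 95% confidence interval for the rate ratio lies below 1.5. On adjustment it states: "The treatment arm and inpatient hospitalization in the prior year will be the only covariates included in the regression model". The variable table there lists no baseline ED or urgent-care measure. Nor does SAP, Baseline Covariates, or the covariate list in Protocol 8.2.1 (age, gender, race, site).

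SAP, Baseline Covariates, explains the hospitalization covariate: it "will be adjusted for in primary analyses as it is prognostic of the outcome and will increase precision".

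Protocol 8.2.1 gives the power for a true ratio of 1 at one-sided alpha 0.025 and 1:1 allocation. For 0.0325 ED visits per month it reads "we estimate 71% power(48) with 400 patients per arm and 67% power with 360 patients per arm"; for 0.05 per month the figures are 88% and 84%. No dispersion parameter or design effect accompanies these figures. The same section justifies the sandwich estimator by "possible violation of the Poisson variance assumption(44") and by clustering within clinics and providers. It applies the approach to ED visits for the same reasons.

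**The concern.** A patient's past ED/urgent-care count is the natural baseline for a future count of the same events. A yes/no inpatient flag misses visits that did not end in admission. Visit counts in a psychiatric population plausibly include repeat visitors. That widens the interval, and a baseline count can recover some of the lost precision.

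This is the trial's only formal non-inferiority test, and it addresses the main foreseeable harm of steering prescribers away from antipsychotics. If the planning powers are optimistic, an inconclusive interval is more likely than the protocol suggests.

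Balance is a second, weaker reason. Patients enter after prescribers are randomized, and intervention prescribers can also enroll a patient by ordering a study service (Protocol 5.2 and Appendix A). Case mix could therefore differ by arm.

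**Working it through.** **Inputs.** From Protocol 8.2.1: margin 1.5, true ratio 1, one-sided alpha 0.025, 400 or 360 per arm, 0.0325 or 0.05 visits per month. Follow-up is 6 months. Variance/mean ratios above 1 are assumptions; the documents give no dispersion figure.

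**Step 1: reproduce the stated power.** Expected events per arm are E = n × 6 × monthly rate. Under pure Poisson variance the log rate ratio has variance 2/E, so

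power = Φ( ln 1.5 / √(2/E) − 1.96 ).

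| Rate/month | n per arm | E | Computed | Stated |
|---|---|---|---|---|
| 0.0325 | 400 | 78.0 | 71.6% | 71% |
| 0.0325 | 360 | 70.2 | 67.1% | 67% |
| 0.05 | 400 | 120 | 88.1% | 88% |
| 0.05 | 360 | 108 | 84.6% | 84% |

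A variant with null-restricted variance gives 71.4%, 67.0%, 87.6% and 84.1%, which round to the stated figures. The stated powers therefore carry no overdispersion and no clustering.

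**Step 2: allow overdispersion.** With variance/mean φ, replace E by E/φ. For example, at 0.0325, n = 360 and φ = 1.4: E/φ = 50.1, 0.4055 × √(50.1/2) = 2.03, and Φ(0.07) = 53%.

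| φ (assumed) | 0.0325, n=360 | 0.0325, n=400 | 0.05, n=360 | 0.05, n=400 |
|---|---|---|---|---|
| 1.0 | 67% | 72% | 85% | 88% |
| 1.2 | 59% | 64% | 78% | 82% |
| 1.4 | 53% | 57% | 71% | 76% |
| 1.7 | 45% | 49% | 63% | 67% |

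A provider-clustering design effect enters the formula the same way. With φ = 1, n = 360 and 0.0325 per month, design effects of 1.1 and 1.2 give 63% and 59%.

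**Step 3: gain from the baseline count.** The right comparator is the SAP's model, which already contains prior hospitalization. Simulations used 360 per arm, 0.39 visits per year, gamma patient heterogeneity, no provider clustering, and prior hospitalization in both models. Where hospitalization was driven by the same patient risk, its assumed prevalence ran from 15% to 35%; some runs set the correlation of past with future risk at 0.7. Gains from adding log(1 + prior-year count), across runs:

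| φ (assumed) | Power gain | Cut in variance of log ratio |
|---|---|---|
| 1.2 | about 0 to 2 points | about 1 to 4% |
| 1.4 | about 2 to 5 points | about 2 to 8% |
| about 1.65 | about 2 to 6 points | about 0 to 15% |

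In one such set (15% prevalence), power moved from 60% to 62%, 56% to 59% and 52% to 56%. With no heterogeneity, adding the count to an arm-only model left power unchanged within simulation error. At a true ratio of 1.5 the false non-inferiority rate was about 2 to 4% in every model, against a nominal 2.5%.

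**The case against.** The strongest reply is that a sparse prespecified model for a secondary outcome is legitimate, and that prior hospitalization already carries much of the crisis history. That is largely right, and it limits the size of the point. Measured against an arm-only model, the gain looks larger: at 360 per arm and variance/mean 1.2, 1.39 and 1.65, power goes from 59% to 61%, 53% to 58% and 46% to 55%. A reader might take those as gains over the plan. They are not, because the plan's model is not arm-only.

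Other stronger readings also fail:

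- **That the SAP contradicts its own reason for adjusting.** That reason is confined to the primary analyses, where the outcome is antipsychotic use. The SAP offers no precision argument for the ED/urgent-care model.
- **That the protocol foresees repeat ED visitors.** Its remark on Poisson variance is written for the antipsychotic-use models and only carried over to ED visits.
- **That the test is simply a 67 to 71% test.** The protocol also gives 84 to 88% at 0.05 per month. The 0.0325 rate is for ED visits alone, whereas the SAP outcome includes urgent care. A higher combined rate could raise power, but the documents give none.
- **That the interval is invalid.** The robust standard error is already specified, and the simulated error rate stayed near nominal. The issue is precision.
- **That the arms differ in crisis history.** The SAP reports a difference in age only.
- **That safety would otherwise go unexamined.** Protocol 10.1 has the DSMB compare ED/urgent-care visits, hospitalizations, suicide attempts and deaths three times a year.

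Timing also matters. The intervention alert was switched off on July 1, 2020, and the SAP was edited through December 2021, so a new covariate may come after outcomes were seen.

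**Conclusion.** The point holds in modest form. The model omits the outcome's own baseline, and the four stated powers are upper limits at the rates they assume because they include neither overdispersion nor clustering. How far true power falls below them is unknown; for variance/mean of 1.2 to 1.7 at 360 per arm it is about 59% to 45% at 0.0325 per month and 78% to 63% at 0.05, before any adjustment.

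Adding the baseline count to the SAP's model should bring about 0 to 6 power points and roughly 0 to 15% lower variance of the log rate ratio. This rests on assumed heterogeneity, on past risk predicting future risk, and on how closely hospitalization tracks visit risk. The stated power is not restored. Under the log link, the covariate leaves the rate-ratio estimand unchanged in a randomized comparison.

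**What to change.** 1. In SAP, Secondary analysis I, add log(1 + number of ED/urgent-care days from day −365 to −1) and the new-enrollee flag to the model, alongside arm and prior hospitalization. If outcomes are already unblinded, keep the current model as the main analysis and report this one as a labelled sensitivity analysis.
2. In Protocol 8.2.1, label the four powers as assuming no overdispersion and no provider clustering, and show a range for assumed variance/mean of 1.2 to 1.7. State that the rate used is ED-only.

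Cost: one extra year of ED/urgent-care extraction and a few sentences. The SAP lists the outcome variable and its offset as absent, so the look-back can be specified when they are built. History will be incomplete for new enrollees, and possibly for Nationwide Children's Hospital patients who are not plan members. The flag handles this only in part: it is based on encounters, so an established patient at that site can pass it and still have unseen visits elsewhere. The report should say so.

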12.3 Protocol Deviations

Site staff will immediately report protocol deviations to the local PM, who will inform the site Investigator or PI. Any deviations will be considered noncompliance with this protocol or Good Clinical Practice. Protocol deviations will include privacy breaches, and IT-related problems that lead to errors in protocol adherence.

Protocol deviations that may impact patient safety or study data integrity will be immediately reported to the KP Washington PI and PM. The DSMB will be informed within 5 business days of KP Washington becoming aware of a protocol deviation impacting patient safety or study data integrity.

Sites will report other protocol deviations as outlined in the QMP, Site IRBs will be notified of deviations per local reporting requirements. The NIMH Contracting Officer's Representative and NIMH DSMB will review protocol deviations in the tri-annual data reports.

Events not considered protocol deviations: Due to the pragmatic and encouragement design aspects of the study, the failure of a provider or patient to adhere to the protocol (e.g., bypassing medication alert, not responding to request for active CAP consult, not following CAP recommendations, refusal or drop out from BH navigation or bridging, not closing a chart note in time for reviews to be conducted), are not considered protocol deviations. These uncontrolled and expected events are of scientific interest due to the pragmatic nature of the study.

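### SAP Secondary analysis I does not carry over the protocol's superiority precondition, or its supplementary as-treated analysis, for the ED/urgent-care non-inferiority claim

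*SAP*

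**What the plan says.** **SAP.** Secondary analysis I fits a Poisson GEE to ED and urgent-care visit counts, with arm and prior-year hospitalization as covariates, and closes with a complete decision rule: "non-inferiority of the intervention will be concluded if the entire coverage of the 95% CI is less than 1.5". The section on the predictor of interest plans intent-to-treat only. Nothing in the SAP makes this test depend on Primary analysis I, and no as-treated or per-protocol analysis appears. The nearest item, a cross-over analysis, is struck through and belonged to Primary analysis II (antipsychotic days). Delivery of services is summarised descriptively in Secondary analyses V and VI.

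**Protocol.** Section 8.2.1 uses the same margin and the same CI criterion, but surrounds them with two further provisions:

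- The non-inferiority test on the ED visit rate "will only be assessed on final analysis if superiority is shown for the primary endpoint of no antipsychotic use at 6 months".
- A supplementary as-treated analysis is to be run, "comparing outcomes according to treatments actually received by patients during their observed period of follow-up". The stated reason is that intent-to-treat becomes anti-conservative for non-inferiority if many intervention patients revert to control.

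Section 12.3 lists, among events that are expected and not counted as deviations, "refusal or drop out from BH navigation or bridging". It treats bypassing the alert and not following the psychiatrist's advice in the same way. The Protocol Summary and section 5.5 make case review by the study psychiatrist automatic for eligible intervention patients.

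**The concern.** A non-inferiority criterion is easiest to meet when the two arms are treated alike. In an encouragement trial, where providers and families may decline most of what is offered, an intent-to-treat rate ratio near 1 can arise because the offer does no harm or because little was taken up. The protocol handles this in two ways. It withholds the claim unless the intervention has been shown to change prescribing, and it asks for a second look by treatment received. An analyst who works from the SAP alone would do neither, and could report non-inferiority after a null primary result, which section 8.2.1 does not allow. What is at stake is a safety statement about ED and urgent-care use in children.

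**Working it through.** **Inputs.** The margin is 1.5 (protocol 8.2.1; SAP Secondary analysis I). The test is planned "with a one-sided 0.025 alpha level with equal allocation between groups", equivalent to the two-sided 95% CI. Monthly control rates: "Using an estimated rate of emergency department visits of 0.0325 per month on control" and "With a greater monthly emergency department rate of 0.05" (protocol 8.2.1). There are 400 patients per arm, or 360 after 10% loss (protocol 8.1), followed for 6 months.

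**Formula.** Expected control events are E0 = n × 6 × rate, and intervention events are E1 = ρ × E0 for true ratio ρ. On the log rate ratio, SE = √[φ(1/E0 + 1/E1)], where φ is a variance inflation factor (φ = 1 for pure Poisson). Then

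P(upper limit < 1.5) = Φ( ln(1.5/ρ)/SE − 1.96 ).

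**Step 1: reproduce the protocol's power (ρ = 1), then double the variance.** ln 1.5 = 0.4055.

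| n per arm | Rate/month | Events per arm | SE (φ = 1) | P, φ = 1 | Protocol | P, φ = 2 |
|---|---|---|---|---|---|---|
| 360 | 0.0325 | 70.2 | 0.1688 | 67.1% | 67% | 39.7% |
| 400 | 0.0325 | 78.0 | 0.1601 | 71.6% | 71% | 43.3% |
| 360 | 0.05 | 108 | 0.1361 | 84.6% | 84% | 55.8% |
| 400 | 0.05 | 120 | 0.1291 | 88.1% | 88% | 60.3% |

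First row: 0.4055/0.1688 − 1.96 = 0.44, and Φ(0.44) = 67%. All four stated figures reproduce within a point. They are also the chance that the SAP rule yields the claim when assignment has no effect on visits. The value φ = 2 is an assumption. The chance drops below 50% once φ exceeds 1.50-1.67 (rate 0.0325) or 2.31-2.57 (rate 0.05).

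**Step 2: add the precondition.** If antipsychotic use is unaffected, the 95% CI in Primary analysis I falls wholly on the favourable side 2.5% of the time. The claim needs that result as well, so its probability is at most 2.5%. If the two tests were independent it would be 0.025 × 0.671 = 1.7% up to 0.025 × 0.881 = 2.2%.

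**Step 3: dilution, as an illustration.** Suppose visits rise by 60% among patients who receive services and a fraction f receives them, so that ρ = 1 + 0.6f. Neither figure is in the documents. With 360 per arm and φ = 1:

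| f | ρ | P at 0.0325 | P at 0.05 |
|---|---|---|---|
| 100% | 1.60 | 0.9% | 0.6% |
| 50% | 1.30 | 14.5% | 20.0% |
| 30% | 1.18 | 31.5% | 45.0% |
| 10% | 1.06 | 55% | 74% |

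**Step 4: what an as-treated comparison can show.** Compare a treated fraction f of the intervention arm with everyone else, at true ratio 1: events are f × E0 and (2 − f) × E0. Over the four planning scenarios, the chance that its CI clears 1.5 is 18-28% at f = 10%, 30-47% at f = 20% and 55-78% at f = 50%. At low uptake it would usually miss the margin even with no harm.

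**The case against.** The strongest reply is that nothing false would be concluded. The trial estimates the effect of assignment. If the true ratio is 1, non-inferiority is the right answer for that estimand, and 67-88% is planned power and not an error rate. That stands: the difficulty is one of interpretation, plus a conflict with the protocol's own rule.

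Further points also stand:

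- Only the superiority requirement is a condition on the claim. The as-treated analysis is supplementary and has no decision rule, and the anti-conservatism argument is given for it alone. The protocol states no reason for the superiority requirement.
- The SAP is silent. A reader might infer that the sponsor chose to remove the provisions, but no passage shows such a decision.
- A reader might also infer that a barely delivered intervention would probably be declared safe. The documents do not support that. They give no uptake figures, and psychiatrist review is automatic in the intervention arm. The partial-delivery results in step 3 pass 50% only at the lowest assumed uptake. The claim would concern ED and urgent-care visits only; hospitalizations, suicide attempts and deaths are compared separately for the DSMB (protocol 10.1). Secondary analyses V and VI would show low uptake to readers.
- The figures assume full enrolment, which the protocol gives as an upper limit. Fewer patients would lower them, while counting urgent-care visits on top of the ED-only planning rate would raise them.

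None of this supplies the missing precondition. The SAP rule is complete as worded, and following it can produce a claim that section 8.2.1 excludes.

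**Conclusion.** The concern holds as a discrepancy between protocol and SAP that changes when a claim is made. With no effect on visits or on antipsychotic use, the SAP rule gives a non-inferiority statement about 67-72% of the time at 0.0325 visits per month and 85-88% at 0.05; the protocol's rule gives it at most about 2.5% of the time. The first range assumes 360-400 patients per arm and Poisson variance, and becomes about 40-60% if the variance is doubled. The loss of the as-treated analysis removes a check on interpretation and does not itself change the decision.

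It would go too far to require that non-inferiority be withheld whenever the as-treated and intent-to-treat results differ. Neither document says so, and step 4 shows that such a rule would often block the claim for lack of precision.

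**What to change.** In SAP Secondary analysis I:

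1. State that non-inferiority is tested and claimed only if Primary analysis I shows lower antipsychotic use in the intervention arm (upper 95% limit of the OR below 1). Otherwise report the rate ratio and CI descriptively. This leaves the DSMB safety comparisons untouched.
2. Report the as-treated rate ratio beside the intent-to-treat ratio, as a supplementary check with no veto. Define treated as at least one navigation call or telemental health session delivered (`trt_stage` 4 or 6). It is safer to build this from the two count variables in Secondary analysis V, because a patient coded 5 may also have had calls. Do not count psychiatrist review, which is automatic and could make nearly the whole intervention arm treated.
3. If the sponsor meant to abandon either provision, record that and the reason.
4. If results already exist, report whether the precondition was met and label any non-inferiority statement made without it as a departure from the protocol.

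The cost is a few sentences and one extra model. The delivery variables are marked present in the SAP; the visit count and its offset are marked absent and are needed in any case. The downsides are that the claim becomes conditional, and that the as-treated estimate is confounded by who accepts services and does not isolate the alert or the psychiatrist review.
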